**INTERMITTENT VERSUS CONTINUOUS SUCTION TECHNIQUE IN THE DIAGNOSIS OF
PANCREATIC SOLID LESIONS. A PILOT STUDY**

STUDY PROTOCOL 03/02/2019

NCT03829748

PRINCIPAL INVESTIGATOR

Dra. [name]

SUB-INVESTIGATORS

[name] [name]

[name] [name]

Gastroenterology Department, Endoscopy Unit

Hospital Universitario de la Princesa

Madrid, Spain

1. INTRODUCTION:

Solid lesions of the pancreas can be neoplastic or non neoplastic and it is important to accurately differentiate between them because of the poor prognosis related to pancreatic neoplasm. There are many types of solid pancreatic lesions: pancreatic adenocarcinoma, neuroendocrine tumor, lymphoma, solid pseudopapillary neoplasm and pancreatic metastasis.

There are several diagnostic methods for the study of pancreatic solid lesions. The different imaging test allow detection and characterization of those lesions, but most times an anatomopathological diagnosis is needed before establishing the most appropriate treatment.

Endoscopic Ultrasound guided fine needle aspiration (EUS-FNA) is the diagnostic method of choice for the diagnosis of these lesions as it detects small lesions that sometimes cannot be found in radiological imaging test, evaluates vascular invasion and the presence of liver metastasis, and allows pancreatic puncture for a cytological diagnosis. EUS-FNA is the safest technique for pancreatic puncture and the least related to needle track seeding.

In order to gather as much material as possible different techniques have been proposed:

- Fanning technique and multiple pass technique: to guide the needle into different regions of the target lesions with or without removing the needle out of the lesion depending on whether the lesion is hard or soft.
- Use of stylet: there are no data clearly demonstrating that the use of suction increases the yield of EUS-FNA. Some authors do slow withdrawal of the stylet.
- Size of the needle: 19 gauge, 22 gauge, 25 gauge, depending on the localization, size and vascularization. There is increasing evidence that smaller needles offer at least similar results in diagnostic yield compared to larger needles and are also easier to manipulate.
- Use of suction: there is conflicting evidence in this point. Several studies have evaluated the use of high volume aspiration vs low volume aspiration, continuous aspiration vs no aspiration and suction with empty syringe vs water-filled syringe but none is clearly better than other.

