2. HIPOTESIS:

Intermittent suction improves the diagnostic yield of pancreatic lesions compared to standard (continuous) suction. Up to our knowledge this method has not been yet evaluated.

3. STUDY DESIGN:

Interventional study with diagnostic purpose, longitudinal, prospective, unicentric, blinded for participant and anatomopathologist, in patients with solid pancreatic lesions with indication of cytological sampling by Endoscopic Ultrasound referred to the Endoscopy Unit of Hospital Universitario de la Princesa from January 2019 to December 2019.

Following clinical practice, an endoscopic ultrasound fine-needle aspiration (EUS-FNA) with a 25 gauge needle will be performed to each participant. The patients will be divided into two arms with a 1:1 ratio:

- a) Intermittent aspiration: Intervention arm. Endoscopic ultrasound will be done for the localization of the lesion and to localize the site of puncture. Prior to the puncture of the lesion the stylet is removed and a vacuum syringe is prepared with 10 cc of vacuum allowing the generation of continuous pressure inside and connected to the end of the needle. Once the lesion is punctured 15 movements in and out of the lesions will be made while the syringe is opened and closed on and off for a total of 3 times each pass. A total of 4 passes will be done in each lesion.
- b) Continuous/standard aspiration: Same procedure but once the lesion is punctured 15 movements in and out of the lesions will be made while the syringe remains opened.

Randomization will be done with the generation of a computer-generated random list using Epidat 4.0. software (SERGAS®, Santiago de Compostela, Spain).

The endoscopic ultrasound will be done with an Olympus linear echoendoscope (GF-UTC 260 Olympus® Tokyo, Japan) under Propofol sedation by an Anesthesiologist.

Each pass will be sent to the pathologist separately to evaluate their individual characteristics and to determine which one is diagnostic. A complete report will be done assessing:

- a) Cellularity
- b) Hematic contamination
- c) Presence of cell block and possibility of doing immunohistochemistry

4. OUTCOME MEASURES:

- a. Primary outcome measure: Increase in diagnostic yield of pancreatic solid lesions
- b. Secondary outcomes:
 - Sample Celularity: Number of malignant cluster of cells on each endoscopic pass
 - Blood contamination: Percentage of blood contamination of the slides
 - Number of passes to reach a positive cytological diagnosis

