5. ELEGIBILITY CRITERIA:

- a) Inclusion Criteria:
 - Pancreatic solid lesion
 - Patients over 18 years old
 - Suitable for endoscopy
- b) Exclusion Criteria:
 - Contraindication for endoscopy
 - Active anticoagulant therapy
 - Thrombocytopenia or coagulopathy in the absence of its correction prior to the procedure
 - Absence of informed consent
 - Pregnancy
 - Not accessible lesion for endoscopic ultrasound puncture

6. STATISTICAL ANALYSIS PLAN:

Data will be expressed as means and standard deviation for quantitative variables or frequencies and percentages for the categorical ones. Variables with non-normal distributions will be represented as means and percentage ranges.

Randomization will be done with a computer-generated random list in a 1: 1 ratio. The chi-square test will be used to compare qualitative variables. Correlation kappa values will be offered between both methods. In order to evaluate the differences in diagnostic yield, the sensitivity after the completion of each pass will be calculated by correlating the continuous values of confusion with the final cytology with the Spearman test. The number of optimal passes depending on the method will be calculated by maximizing that the following passes would not modify the additional diagnostic yield more than 10% over the accumulated one. On the other hand, the cellularity and blood contamination graduated in its three levels will be contrasted between both methods with an analysis of McNemar. All the variables that could potentially modify the diagnostic yield of both methods will be compared with univariate and later multivariate analysis by means of logistic regression analysis with the STATA application (v13.0, StataCorp, College Station, Texas, USA). The protocol will be approved by the Ethical Committee of the Hospital Universitario de la Princesa before the start of the study.

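### The only analysis named for the yield comparison is a Spearman correlation, which gives neither a sensitivity nor a between-arm difference, moves with case mix and can rank the arms wrongly

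*Combined protocol and SAP*

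**What the plan says.** Section 2 states a between-arm superiority hypothesis: "Intermittent suction improves the diagnostic yield of pancreatic lesions compared to standard (continuous) suction". Section 3 sets up a parallel-group comparison ("The patients will be divided into two arms with a 1:1 ratio") with four passes per lesion, each read separately by the pathologist. Section 4 gives the endpoint: "Primary outcome measure: Increase in diagnostic yield of pancreatic solid lesions". Yield is not defined further.

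In section 6, one sentence states the purpose of evaluating yield differences. It begins "In order to evaluate the differences in diagnostic yield, the sensitivity after the completion of each pass" and continues "will be calculated by correlating the continuous values of confusion with the final cytology with the Spearman test". The values to be correlated are not defined. No effect measure, confidence interval or between-arm test is attached to the sentence.

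Elsewhere in section 6, "The chi-square test will be used to compare qualitative variables" is a general line not tied to any endpoint, and logistic regression is planned for factors that might modify yield.

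**The concern.** There are three faults in the sentence that serves the primary question.

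- **Wrong quantity.** A correlation coefficient is not a sensitivity. Sensitivity is in turn not yield, which section 4 names as primary.
- **No contrast.** Rho measures association within a set of patients. Its p-value tests rho = 0, whereas the hypothesis concerns intermittent against continuous suction.
- **Dependence on case mix.** The introduction notes that "Solid lesions of the pancreas can be neoplastic or non neoplastic", and section 5 admits any solid lesion. The share of malignant lesions can therefore differ by chance between small arms, and rho moves with that share even when sensitivity does not.

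Followed literally, the trial would report for its main question a number that is not the yield and does not test the hypothesis. A chance difference in case mix could look like a suction effect or hide one.

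**Working it through.** The plan states no sample size, alpha, power or expected sensitivity, so there is no planned figure to reproduce. Sensitivity (Se), specificity (Sp), malignant share (π) and patients per arm (n) below are all assumptions.

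**Formula.** For a positive/negative pass result against a positive/negative reference, rho equals phi:

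rho = (Se + Sp − 1) × √[π(1−π) / (q(1−q))], with q = πSe + (1−π)(1−Sp).

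With Sp = 1 this reduces to rho = √[Se(1−π) / (1−πSe)]. At Se 0.85 and π 0.80, the formula and a direct Spearman calculation on the 2×2 data both give 0.729.

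**1. Same sensitivity, different rho (Sp = 1).**

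| Se | π = 0.50 | 0.60 | 0.70 | 0.80 | 0.90 | 0.95 |
|---|---|---|---|---|---|---|
| 0.80 | 0.816 | 0.784 | 0.739 | 0.667 | 0.535 | 0.408 |
| 0.90 | 0.905 | 0.885 | 0.854 | 0.802 | 0.688 | 0.557 |

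For example, Se 0.80 and π 0.80 give √(0.16/0.36) = 0.667. If every patient in an arm is reference-positive, rho is undefined although sensitivity can still be estimated.

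**2. Reversed ranking.**

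- Through case mix: Se 0.90 at π 0.90 gives √(0.09/0.19) = 0.688, while Se 0.80 at π 0.70 gives √(0.24/0.44) = 0.739.
- Through specificity at equal π = 0.80: Se 0.90 with Sp 0.80 gives 0.656, while Se 0.85 with Sp 1 gives 0.729.

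**3. Size of chance imbalance.** At 30 per arm and π = 0.80, the 95% range for the difference in malignant share is ±1.96 × √(2 × 0.8 × 0.2/30) = ±0.202, about 20 points.

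**4. Simulation.** Each setting had 100,000 trials, with true Se 0.90 against 0.80, Sp 1, and the same underlying π (0.70 to 0.90) in both arms.

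| n per arm | rho orders the arms opposite to observed sensitivity | rho contradicts the true order | observed sensitivity contradicts the true order |
|---|---|---|---|
| 20 | 14–17% | 23–24% | 18–21% |
| 40 | 10–17% | 17–20% | 11–14% |
| 100 | 4–9% | 6–9% | 3–5% |

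The rho columns count only trials where rho was defined in both arms. At 20 per arm and π = 0.90 it was undefined in at least one arm in 23% of trials.

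**5. A graded score does not help.** In a constructed set of 40 patients, an order-preserving rescaling of the score left rho at 0.724, while sensitivity at a fixed cut-off fell from 28/32 = 87.5% to 20/32 = 62.5%.

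**6. If final cytology means the combined result of the same four passes.** The wording allows this, and no surgical or follow-up reference is described. After pass 4 the test is then its own reference, so rho is 1 or undefined in both arms. At earlier passes π is the arm's own final yield, so a higher yield lowers rho. If pass 1 finds 80% of final positives in both arms and final yield is 90% against 70%, rho is 0.535 against 0.739. The better arm looks worse without any chance imbalance.

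**7. Direct analysis of assumed counts (40 per arm).** Arm A detects 32 of 36 malignant lesions and arm B 25 of 30, with no false positives.

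- Spearman: 0.667 against 0.745, which favours B.
- Sensitivity: 88.9% against 83.3%, difference +5.6 points (Wald 95% CI −11.3 to +22.4), which favours A.
- Yield, if diagnostic means positive: 32/40 = 80.0% against 25/40 = 62.5%, difference +17.5 points. The Wald 95% CI is 0.175 ± 1.96 × √(0.8×0.2/40 + 0.625×0.375/40), or −2.0 to +37.0 points.

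**The case against.** The strongest reply is that section 6 labels no analysis as primary and already lists valid tools. A yes/no yield is a qualitative variable, so an analyst could apply chi-square to it without contradicting the plan, and logistic regression is also available. That stands as a reason why repair is easy. It does not supply a primary analysis: neither tool is assigned to yield, and the one sentence that addresses yield differences names another method.

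The phrase about confusion may be a translation of confusion-matrix values. If so, the yes/no model above is not quite what was meant. Sensitivity would then come straight from the counts, Spearman would have no role, and the sentence would still need rewriting.

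The reversal example is fairly called extreme. With 30 per arm and 80% malignant, an imbalance of at least 20 points toward the better arm has probability about 3.7%. With 85% against 75% malignant, Se 0.90 against 0.80 keeps the right order (0.758 against 0.707). At equal shares and Sp 1, rho always rises with sensitivity. This limits how often rankings go wrong; it does not make rho a sensitivity or a contrast.

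Finally, yield also depends on case mix if diagnostic means positive. At Se 80% it is 48%, 56%, 64% and 72% for malignant shares of 60% to 90%. Under randomisation, however, the risk difference is unbiased and its interval covers chance imbalance. The Spearman step has no corresponding between-arm estimate or interval.

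**Conclusion.** The concern holds and must be fixed. That a Spearman coefficient is neither a sensitivity nor a between-arm comparison follows from definitions and needs no assumed figures. The size of the distortion does rest on assumptions. At Se 0.80 and Sp 1, rho falls from 0.78 to 0.53 as the malignant share goes from 60% to 90%. In the simulations it ordered the arms against their observed sensitivities in 4% to 17% of trials, for 20 to 100 patients per arm. Wrong ranking requires a difference in case mix or specificity between arms, or a reference built from the same passes. Pilot status does not remove the problem, because a pilot still has to report an interpretable yield in each arm.

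**What to change.** Delete the Spearman step and replace the sentence in section 6 with the following.

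- **Primary analysis:** the proportion of randomised, punctured patients with a diagnostic cytology after all passes, compared between arms as a risk difference with a 95% confidence interval (Newcombe or Miettinen-Nurminen).
- **Test:** the chi-square test already listed, or an exact test if any expected count is below 5.
- **By pass:** cumulative yield and sensitivity after passes 1 to 4, as proportions with 95% confidence intervals for each arm.

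It would also help to define a diagnostic cytology and to state what final cytology is. If it is the combined result of the four passes, sensitivity after pass 4 is 100% by construction.

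For the primary analysis the cost is SAP wording only, since each pass is already read separately. If sensitivity is wanted against a reference independent of the passes, that reference has to be specified, and the documents do not describe its collection.

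### The optimal number of passes per method rests on a bare 10% cut-off with no measure of uncertainty; unless first-pass yield is very high, identical techniques can readily receive different numbers

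*Combined protocol and SAP*

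**What the plan says.** Section 3 (Study Design) fixes the number of passes: "A total of 4 passes will be done in each lesion". It also makes a result available for every pass: "Each pass will be sent to the pathologist separately".

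Section 6 (Statistical Analysis Plan) then sets three relevant analyses:

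- "In order to evaluate the differences in diagnostic yield", sensitivity is to be obtained after each pass by "correlating the continuous values of confusion with the final cytology with the Spearman test".
- "The number of optimal passes depending on the method" is to be found by "maximizing that the following passes would not modify the additional diagnostic yield more than 10% over the accumulated one".
- In general, "The chi-square test will be used to compare qualitative variables".

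No interval, bootstrap or other precision measure is attached to the optimal number, and no denominator is given for the sensitivity. Section 4 (Outcome Measures) does not list the optimal number. It lists a related per-patient quantity: "Number of passes to reach a positive cytological diagnosis". The title calls the study a pilot. The documents state neither a sample size nor an expected yield.

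**The concern.** The result for each arm can only be 1, 2, 3 or 4, and it turns on whether an observed gain falls just above or just below 10%. In a small arm one patient can move it. The trial compares two methods, so its report would set two such numbers side by side. A pair such as 2 and 3, with nothing to show how firm either is, invites the reading that one technique needs fewer passes.

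Two further problems feed into this. First, the rule needs a cumulative proportion of patients diagnosed, but the per-pass sensitivity is to come from a rank correlation. A correlation coefficient is not the share of patients diagnosed by a given pass. Second, the rule can be read in more than one way, so two analysts following the plan could report different optima from the same data.

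**Working it through.** The plan gives no figure to reproduce. Inputs from the documents: four passes per lesion, 1:1 parallel arms, a 10% cut-off. Assumptions: patients per arm in the denominator (n), and the cumulative yield curve. Throughout, the optimum is the smallest number of passes k that qualifies, or 4 if none of 1 to 3 does.

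**1. The reading matters.** Take 18/20/21/23 of 30 patients diagnosed after passes 1 to 4.

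| Reading | Check | Optimum |
|---|---|---|
| Relative, singly | k=1: 2/18 = 11.1%, fails. k=2: 1/20 = 5.0% and 2/21 = 9.5%, qualifies | 2 |
| Relative, together | k=1: 5/18 = 27.8%, fails. k=2: 3/20 = 15%, fails. k=3: 2/21 = 9.5%, qualifies | 3 |
| Absolute, singly | k=1: 2/30 = 6.7, 1/30 = 3.3, 2/30 = 6.7 points, qualifies | 1 |
| Absolute, together | k=1: 5/30 = 16.7 points, fails. k=2: 3/30 = 10.0 points, qualifies | 2 |

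Relative to the accumulated yield is the more natural reading of the text.

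**2. One patient can move the number.** Relative, singly, n = 30:

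- 18/22/24/25: k=1 fails (4/18 = 22.2%); k=2 qualifies (2/22 = 9.1%, 1/24 = 4.2%). Optimum 2.
- 18/22/25/26, which is one more patient diagnosed on pass 3: k=2 fails (3/22 = 13.6%); k=3 qualifies (1/25 = 4.0%). Optimum 3.

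Counted together and relative, both arms give 3, so this example depends on the reading. The simulation in step 4 does not.

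**3. The sensitivities behind those two numbers barely differ.** With Wilson limits (l, u) for each arm, Newcombe's interval for d = p2 − p1 is

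- lower: d − √[(p2 − l2)² + (u1 − p1)²]
- upper: d + √[(u2 − p2)² + (p1 − l1)²]

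Pass 1: both arms 18/30 = 0.600, Wilson 0.423 to 0.754, so the margin is √(0.177² + 0.154²) = 0.235.

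| Pass | Difference (points) | 95% CI | Half-width |
|---|---|---|---|
| 1 | 0.0 | −23.5 to 23.5 | 23.45 |
| 2 | 0.0 | −21.7 to 21.7 | 21.7 |
| 3 | 3.3 | −16.6 to 23.0 | 19.8 |
| 4 | 3.3 | −15.5 to 22.0 | 18.8 |

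The half-widths run from about 19 to 23 points. Resampling patients in the first arm gives an optimum of 1/2/3/4 in 9/50/33/8% of bootstrap samples, so the reported 2 recurs only half the time.

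**4. How often identical techniques differ.** 40,000 simulated pairs of identical arms per setting. Each patient's first diagnostic pass (1 to 4, or never) is drawn from a multinomial, and the cut-off is compared in exact integers. Three mid-range cumulative curves were used: 60/72/79/83, 70/80/85/88 and 50/65/75/80%. Ranges below cover the three curves and both relative readings.

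| n per arm | Different numbers | Two or more passes apart |
|---|---|---|
| 20 | 58–71% | 10–27% |
| 30 | 51–67% | 6–21% |
| 50 | 42–64% | 2–15% |
| 100 | 26–55% | 0.3–6% |

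With the two absolute readings added, the range at 20 to 50 per arm is about 40 to 71%. The two relative readings disagree with each other on the same arm in roughly 12 to 35% of arms at these sizes. On these curves the observed optimum recurs in a median of 58 to 70% of bootstrap resamples.

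**5. Where the effect shrinks.** At n = 30:

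- 90/95/96/97%: about 32–47% on the relative readings and 12–26% on the absolute ones.
- 95/98/99/99.5%: about 12–26% relative and no more than 9% absolute.

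**The case against.** The strongest reply is that little hangs on this number. It is not a listed outcome, all four passes are done regardless, and no test or decision uses it. Section 6 also plans sensitivity after each pass and chi-square tests, so some between-arm comparison exists. The per-patient outcome in Section 4 is a better basis for asking whether one method needs fewer passes. The SAP states no interval for any result, so this is one case of a general gap. All of that stands, and it caps the weight of the point. It does not remove it: the plan will still produce an unqualified number per method, and the per-pass sensitivity that might put it in context is not computed as a proportion.

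Three stronger readings are tempting, and the documents do not support them:

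- A reader might infer that the trial will declare the methods different whenever the two numbers differ, making the rates above a type I error. The plan states no such rule.
- A reader might infer that disagreement is frequent at pilot size whatever the yield. The plan states neither arm size nor yield, and with very high first-pass yield disagreement becomes uncommon.
- A reader might take the word for maximizing literally and conclude that the rule always returns 4, since nothing follows the fourth pass. That would make the sentence pointless; it is loose wording for the smallest number that suffices.

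The Spearman step and the missing denominator are also defects of the yield analysis in their own right. They count here only because the cut-off needs a cumulative proportion as its input.

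**Conclusion.** The concern holds in a limited form and is minor. Section 6 gives a fixed 10% cut-off with no uncertainty, open to at least four readings, and describes per-pass sensitivity by a method that does not yield a proportion. The absence of a precision measure and the ambiguity follow from the text alone. The size does not: the 40 to 71% range assumes first-pass yield of 50 to 70% and 20 to 50 patients per arm, and it falls well below that when the first pass already finds nearly every diagnosis. What is at risk is the interpretation of a descriptive summary. The listed outcomes do not depend on it.

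**What to change.** 1. Compute cumulative sensitivity after each pass as a proportion: patients diagnosed by that pass over one stated denominator common to all four passes, replacing the Spearman correlation. Make the between-arm comparison the difference at each pass with its 95% CI, read as four correlated estimates and not as four tests.
2. Define the optimum as the smallest k for which the later passes (state singly or together) add no more than 10% relative to the yield accumulated at k, and 4 if none of 1 to 3 qualifies.
3. Report the optimum as descriptive, with the share of patient-level bootstrap resamples giving 1, 2, 3 or 4 in each arm. Draw no conclusion that one method needs fewer passes from the two point values alone.

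The cost is a few sentences of SAP text and one bootstrap run; the per-pass data are already to be collected. The price is a less definite statement about the optimal number, and wide intervals: mean half-width 13 to 28 points at 20 to 50 per arm under identical techniques. If the four intervals were misread as tests, at least one would exclude zero in about 10 to 13% of such trials, which is why step 1 must say how they are to be read.

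### McNemar and kappa between the two suction techniques need paired results, but each patient is randomised to one technique only

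*Combined protocol and SAP*

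**What the plan says.** Section 3 (Study design) sets up two parallel groups: "The patients will be divided into two arms with a 1:1 ratio". In the intervention arm the syringe is opened and closed during each pass. The control arm is described as "Same procedure but once the lesion is punctured 15 movements in and out of the lesions will be made while the syringe remains opened". On the number of passes it says "A total of 4 passes will be done in each lesion", and on reading them, "Each pass will be sent to the pathologist separately to evaluate their individual characteristics".

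Section 6 (Statistical analysis plan) repeats the allocation: "Randomization will be done with a computer-generated random list in a 1: 1 ratio". It then gives three instructions that bear on this point:

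- a general rule: "The chi-square test will be used to compare qualitative variables";
- an agreement statistic, with no variable named: "Correlation kappa values will be offered between both methods";
- a specific rule for two secondary outcomes: "the cellularity and blood contamination graduated in its three levels will be contrasted between both methods with an analysis of McNemar".

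**The concern.** McNemar's test compares two results on the same unit and uses only the units where the two disagree. Kappa measures how often two results on the same unit agree beyond chance. Both start from a cross-table of technique A against technique B within the same lesion. If each lesion is sampled by one technique only, that table cannot be filled.

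There are two further difficulties. Classical McNemar takes two categories, and these outcomes have three; the three-level extension (Stuart-Maxwell) still needs pairs and ignores the order of the grades. Each lesion also yields four separately read passes, and Section 6 does not say whether the graded comparison counts passes or patients.

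Two of the three listed secondary outcomes, cellularity and blood contamination, are at stake. The kappa sentence names no variable. The sentence after it concerns diagnostic yield, so a reader could take kappa as applying to yield as well.

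**Working it through.** **Step 1. Does the design produce pairs?** The documents give no sample size or rates for these outcomes, so there is no figure to reproduce, and the answer comes from the text.

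| Needed for McNemar or kappa between techniques | What Section 3 provides |
|---|---|
| Both techniques on each lesion | One technique per patient, set by arm |
| Or matched patients across arms | A 1:1 random list; no matching described |
| Or passes alternating between techniques | Four passes per lesion, all with the arm's technique |

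The four passes are repeats within one technique, so they do not pair the techniques. The number of genuine pairs is zero.

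**Step 2. What happens if pairs are invented, three levels?** Assumed data: 30 patients per arm, grades 4/9/17 in one arm and 10/11/9 in the other. Keep each patient's grade fixed and consider every way of pairing the arms. This gives 770 possible 3×3 tables, each weighted by its probability under random pairing.

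- Stuart-Maxwell: p is 0.029, 0.086 and 0.155 at the 2.5th, 50th and 97.5th percentiles; 87% of pairings give p above 0.05.
- Unpaired chi-square (expected 7/10/13 per arm): 2×(3²/7) + 2×(1²/10) + 2×(4²/13) = 2.571 + 0.200 + 2.462 = 5.233 on 2 df, p = 0.073 whatever the list order.
- Wilcoxon rank-sum: U = (17×10 + 17×11 + 9×10) + ½(4×10 + 9×11 + 17×9) = 447 + 146 = 593 out of 900, p = 0.024 whatever the list order.

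**Step 3. The same with two levels.** Assumed data: 24/30 against 15/30. If k pairs have both patients positive, the discordant counts are 24−k and 15−k, and the probability of k is C(24,k)·C(6,15−k)/C(30,15).

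| k | Discordant | Probability | Exact McNemar p |
|---|---|---|---|
| 9 | 15 v 6 | 0.8% | 0.078 |
| 10 | 14 v 5 | 7.6% | 0.064 |
| 11 | 13 v 4 | 24.1% | 0.049 |
| 12 | 12 v 3 | 34.9% | 0.035 |
| 13 | 11 v 2 | 24.1% | 0.023 |
| 14 | 10 v 1 | 7.6% | 0.012 |
| 15 | 9 v 0 | 0.8% | 0.004 |

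The share of pairings above 0.05 is 0.8% + 7.6% = 8.4%. Fisher's exact test on the same counts gives 0.029.

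**Step 4. Does arbitrary pairing create false positives?** No, not to a material degree. With 20 to 50 per arm, type I error at nominal 5% is 1.4–3.0% for exact McNemar, 4.2–5.4% for the uncorrected version and 3.2–4.9% for Stuart-Maxwell.

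**Step 5. What does it cost in power?** Simulated with 30 per arm, a 30/40/30% grade mix, a latent shift of 0.5 SD and four passes per patient:

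| Latent within-patient correlation | Stuart-Maxwell, one rounded grade, random pairs | Wilcoxon, same rounded grade | Wilcoxon, mean grade |
|---|---|---|---|
| 0.3 | 0.45 | 0.62 | 0.72 |
| 0.5 | 0.38 | 0.53 | 0.62 |
| 0.7 | 0.34 | 0.46 | 0.53 |

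**Step 6. What does kappa show?** κ = (observed − expected agreement)/(1 − expected agreement). For unrelated patients observed agreement equals chance agreement on average, so κ centres on 0. Simulated at 30 per arm: identical techniques (80% v 80%) give mean 0.00, 95% range −0.27 to 0.38; different techniques (90% v 60%) give mean 0.00, range −0.24 to 0.27. It cannot tell the two situations apart.

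**Step 7. Why the unit must be stated as well.** Section 6 neither states nor excludes pooling of passes. If all four were pooled as independent in a three-level chi-square at 30 per arm, type I error would be about 12%, 18% and 25% at latent correlation 0.3, 0.5 and 0.7. This is a conditional remark and not part of the defect itself.

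**The case against.** The strongest reply has five parts.

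- **Chi-square is already in the plan.** It is, as a general rule. The later sentence names McNemar for these two outcomes, and the specific instruction governs.
- **Kappa may have been meant against the final cytology.** That would be a legitimate analysis, and the sentence names no variable. But its literal wording is between the techniques, and in that form it means nothing here. If agreement with the final cytology was intended, it should be written as such.
- **Nobody would really pair strangers.** This is plausible, and with unequal arms the test could not be run at all without dropping patients. The likelier outcome may be an unspecified substitute chosen after the data are seen. That is another reason to correct the text; it does not rescue it.
- **The three-level example mixes pairing with use of grade order.** This stands in part. The correct unpaired chi-square is also above 0.05 (0.073), so the contrast with Wilcoxon's 0.024 comes largely from using the order of the grades. The spread of 0.029 to 0.155 on fixed data comes from pairing alone.
- **The three levels are undefined.** This also stands. Section 4 defines the outcomes as a count of malignant clusters and a percentage of blood, while Section 6 uses three levels without cut points. Any graded analysis needs them.

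**Conclusion.** The concern holds. As written, McNemar for cellularity and blood contamination and kappa between the techniques are both wrong for this parallel-group design, because no lesion is assessed under both. This conclusion rests on the design text alone and needs no assumed numbers.

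The sizes above rest on assumed arm sizes, counts, rates and correlations. They illustrate an arbitrary p-value, conservatism in the exact test, lower power and an uninformative kappa. They do not show inflated false positives. McNemar touches secondary outcomes of a pilot study, so this should be fixed but does not by itself undermine the primary comparison.

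**What to change.** In Section 6, replace the McNemar sentence, for cellularity and for blood contamination, with wording such as: *Each patient's grade is the mean of his or her graded passes, with the three levels scored 0, 1, 2 (equal spacing assumed). The arms are compared by the two-sided Wilcoxon rank-sum test, with the patient as the unit.* State the cut points that turn the count and the percentage in Section 4 into the three levels. Delete kappa between the techniques. Any additional pass-level analysis should use patient-clustered standard errors.

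In simulation (20, 30 or 50 per arm, latent correlation 0.3 to 0.7, three grade mixes, 27 scenarios) the proposed test had type I error of 4.2–5.5%.

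The cost is SAP wording. The per-pass reports and three-level grades are already planned, and the rank-sum test is in the Stata version already named. The one drawback is the equal-spacing assumption, which matters little: scoring the levels 0, 1, 3 or 0, 2, 3 changed the decision at 0.05 in 0.7–5.1% of simulated trials. Ordinal logistic regression with patient-clustered errors would be an acceptable alternative.
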